Safety Assessments:	Reactogenicity will be assessed daily on each vaccination day and the following 7 days via collection of solicited local adverse events (AEs; injection site pain, redness, swelling, and itching) and systemic AEs (fever, headache, fatigue, chills, myalgia, arthralgia, nausea/vomiting, and diarrhea) using diary cards (electronic or paper). In addition, other indicators of safety will be collected (e.g., body temperature). Diaries will also be used for collection of unsolicited AEs on each vaccination day and the following 28 days. In addition, subjects will receive a prompt (by e.g., a phone call or text message) to verify whether the subjects had any health concerns since the last visit. Subjects with any Grade 3 solicited or unsolicited AEs reported electronically by the subject will be contacted by the Investigator, and subjects who did not enter any diary information will be prompted and then contacted in case of non-response within 24 hours. Unscheduled visits will be performed when deemed necessary for safety assessments or to ensure data integrity. SAEs, adverse events of special interest (AESIs), and AEs leading to vaccine withdrawal or trial discontinuation will be collected throughout the trial. Non-serious intercurrent medical conditions that may affect the immune response to vaccination will also be collected throughout the trial. AESIs to be monitored throughout the trial include potential immune-mediated diseases (pIMDs) and COVID-19 disease. In case of confirmed COVID-19 disease, a disease-specific diary will be completed by the subject and/or the treating health care provider.
Laboratory Testing for COVID-19 Disease:	As a baseline assessment, a reverse transcription polymerase chain reaction (RT-PCR) test for SARS-CoV-2 will be performed in all subjects. Testing will be done for SARS-CoV-2 spike protein to evaluate vaccine-induced immune responses as well as for SARS-CoV-2 N-antigen (not contained in the vaccine construct) to evaluate immune responses induced by natural infection. This will allow to retrospectively define the subject's serology status, including the baseline status for the by-group/cohort analysis. Subjects will be prompted once or twice per week to report if the subjects have any of the following symptoms: cough, shortness of breath, difficulty breathing, fever $\geq 37.8^{\circ}\text{C}$, fatigue, myalgia, chills, wheezing, nasal congestion, runny nose, sore throat, headache, diarrhea, or new olfactory

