9.1.1.2 Unsolicited Adverse Events and Serious Adverse Events

Diaries will also be used for collection of unsolicited AEs on each vaccination day and the following 28 days. In addition, subjects will receive a prompt (by e.g., a phone call or text message) to verify whether the subjects had any health concerns since the last visit.

The occurrence of AEs (serious and non-serious) will be assessed by non-directive questioning of the subject at each visit. AEs volunteered by the subject during or between visits in the diary or detected through observation, physical examination, laboratory test, or other assessments during the entire trial, will be recorded in the eCRF, if they fall within

the reporting period. Subjects should be instructed to report immediately any AEs with serious symptoms, subjective complaints or objective changes in their well-being to the Investigator or the site personnel, regardless of the perceived relationship between the event and the trial vaccine.

The Investigator will assess the relationship between trial vaccine and each occurrence of each AE/SAE.

SAEs and AEs leading to vaccine withdrawal or trial discontinuation will be collected throughout the trial. Non-serious intercurrent medical conditions that may affect the immune response to vaccination will also be collected throughout the trial.

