10 STATISTICAL CONSIDERATIONS

Due to the exploratory nature of this trial, only descriptive statistics will be used. No confirmatory statistical inference will be performed.

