### 10.5.3 Unsolicited Adverse Events

Unsolicited AEs occurring on the day of vaccination and the following 28 days will be collected. For unsolicited AEs occurring on the day of dose 2 and the booster dose the following rule will be used:

If the AE is occurring on the day of dose 2 but before vaccination the AE will be presented with AEs for dose 1, if the AE is occurring on day of dose 2 but on or after vaccination it will be presented with AEs for dose 2. If this rule cannot be applied (for example, if the start time of the AE is missing) but the AE occurred on the day of vaccination for dose 2 it will be presented with the AEs for dose 2. The same rule applies for any unsolicited AE occurring on the day of the booster dose.

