#### 10.5.6 Medically Attended Adverse Events

Medically attended AEs will be collected on the eCRF throughout the trial.

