### 12.8.1 Analysis of Unsolicited and Solicited AEs

An overall summary of unsolicited AEs will be prepared for AEs occurring within 28 days after each dose, within 28 days after any dose, and all reported AEs (including those reported at more than 28 days after any dose), presenting the number and percentage of subjects with

---

- Unsolicited AEs
- related unsolicited AEs
- grade 3 (severe) unsolicited AEs
- grade 3 (severe) related unsolicited AEs
- SAEs (includes solicited AEs)
- related SAEs (includes solicited AEs)
- intercurrent medical conditions affecting immune response (includes solicited AEs)
- AESIs (includes solicited AEs)
- related AESIs (includes solicited AEs)
- medically attended AEs (includes solicited AEs)
- related medically attended AEs (includes solicited AEs)
- AEs leading to vaccine withdrawal (includes solicited AEs)
- AEs leading to withdrawal from trial (includes solicited AEs)

The overall summary will also be presented by sex (female/male) for any dose regardless of retrospective serology status at baseline.

The following summaries of AEs by SOC and PT will further be provided, separately for AEs occurring within the first 28 days after each vaccination, within the 28 days after any vaccination, and all reported AEs (including those reported at more than 28 days after any dose) if not otherwise stated:

- Occurrence of unsolicited AEs
- Occurrence of related unsolicited AEs
- Occurrence of unsolicited AEs by maximum severity (mild / moderate / severe)
- Occurrence of related unsolicited AEs by maximum severity (mild / moderate / severe)
- Occurrence of SAEs (includes solicited AEs)
- Occurrence of related SAEs (includes solicited AEs)
- Occurrence of SAEs by maximum severity (mild / moderate / severe) (includes solicited AEs)
- Occurrence of related SAEs by maximum severity (mild / moderate / severe) (includes solicited AEs)
- Occurrence of intercurrent medical conditions affecting immune response (includes solicited AEs)
- Occurrence of AESIs (includes solicited AEs)
- Occurrence of related AESIs (includes solicited AEs)
- Occurrence of medically attended AEs (includes solicited AEs)
- Occurrence of related medically attended AEs (includes solicited AEs)
- Occurrence of AEs leading to vaccine withdrawal (includes solicited AEs)
- Occurrence of AEs leading to withdrawal from trial (includes solicited AEs)
- Occurrence of AEs related to SMQs as defined in Section 10.5.9 (includes solicited AEs)

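### Protocol and SAP contradict themselves on whether medically attended and other non-serious unsolicited AEs are collected beyond 28 days after a dose, so the whole-trial AE percentages in SAP 12.8.1 may be incomplete

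*Protocol*

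**What the plan says.** **Passages that set a 28-day window**

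- Protocol 9.1.1.2: "Diaries will also be used for collection of unsolicited AEs on each vaccination day and the following 28 days".
- SAP 10.5.3: "Unsolicited AEs occurring on the day of vaccination and the following 28 days will be collected".
- The primary endpoint for unsolicited AEs (protocol 4.2.1) uses the same 28 days after Day 1 and Day 29.
- The exceptions are listed by type. The synopsis says "SAEs, adverse events of special interest (AESIs), and AEs leading to vaccine withdrawal or trial discontinuation will be collected throughout the trial", and 9.1.1.2 adds "Non-serious intercurrent medical conditions that may affect the immune response to vaccination will also be collected throughout the trial". Footnote l to Table 1 gives the same four types.

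**Passages that assume collection throughout**

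- Protocol Table 1 marks unsolicited AEs at contacts well beyond the 28-day windows.
- SAP 10.5.2 refers to the collection of all AEs over the whole trial.
- SAP 10.5.6: "Medically attended AEs will be collected on the eCRF throughout the trial".
- SAP 12.8.1 plans three sets of tables: 28 days after each dose, 28 days after any dose, and "all reported AEs (including those reported at more than 28 days after any dose". Unsolicited and medically attended AEs appear in all three, in the overall summary and by SOC and PT.

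SAP 12.8 bases percentages on the number of subjects in the analysis set, with no adjustment for time under collection. The protocol does not name medically attended AEs, and SAP 6.1 (changes from protocol) does not mention them.

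**The concern.** A whole-trial percentage with all subjects in the denominator reads as about 13 months of safety experience. That reading is fair only if the event type was sought and recorded in the same way for the whole period. Here one group of passages tells a site to stop recording ordinary unsolicited AEs 28 days after a dose, and another tells it to continue. Two sites could follow different passages in good faith and feed the same table.

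Two things are at stake. First, low late counts could reflect non-collection rather than absence of events. Second, if the 28-day limit governed, boosted subjects had a longer period in scope than unboosted subjects. Only CVnCoV recipients are boosted, so the table columns would not be on equal terms.

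**Working it through.** **Step 1. Do the passages pointing to whole-trial collection settle the matter?**

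| Passage | Points to whole-trial collection | Qualification |
|---|---|---|
| Protocol Table 1, unsolicited AE row | Marks at late contacts | Footnote k says these AEs are recorded in diaries, and the diary window is 28 days |
| Protocol 9.1.1.2, questioning at visits | "The occurrence of AEs (serious and non-serious) will be assessed by non-directive questioning of the subject at each visit" | Entry in the eCRF is conditional on a reporting period; for ordinary non-serious AEs the only period given there is the diary window |
| Protocol Appendix 10, observation period | Consent to end of trial | Refers back to Section 9.1.1 |
| SAP 10.5.2 and 10.5.6 | Throughout the trial | SAP 10.5.3 says 28 days, and SAP 6.1 declares no departure |

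The extracted Table 1 may have shifted cells, so I rely on counts and not positions. The table has 18 day columns. Four of them (Day 120, Day 270 and two for Day 393) lie outside every 28-day window on any schedule, which leaves 14. The unsolicited row carries 18 marks. Even if one mark is an artefact, at least 17 − 14 = 3 fall on those four columns. The conflict with the text is therefore not an extraction effect.

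**Step 2. How much follow-up lies inside the windows?**

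Inputs: doses on Days 1 and 29, booster on Day 57 or Day 180 (protocol Table 2), window from dose day d to d + 28, and last contact on Day 393. As a check, 393 / 30.44 = 12.9 months, in line with the stated 13.

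- No booster: Days 1–29 and 29–57 together are Days 1–57, 57 days. 57 / 393 = 14.5%.
- Day 57 booster: adds Days 57–85, so Days 1–85, 85 days. 85 / 393 = 21.6%.
- Day 180 booster: adds Days 180–208 (29 days), so 57 + 29 = 86 days. 86 / 393 = 21.9%.

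The plan has 603 + 10 + 10 + 40 = 663 subjects, of whom 30 receive the Day 57 booster and 60 the Day 180 booster:

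- Days in window: 573 × 57 + 30 × 85 + 60 × 86 = 40,371.
- Planned days: 663 × 393 = 260,559.
- Inside: 40,371 / 260,559 = 15.5%. Outside: 84.5%.

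By treatment, the mean time in window is (513 × 57 + 30 × 85 + 60 × 86) / 603 = 61.3 days for CVnCoV and 57 days for control. A boosted subject has 85 / 57 = 1.49 to 86 / 57 = 1.51 times the in-scope time of an unboosted one.

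These are nominal shares before dropout and before the safety censoring after unblinding in SAP 10.8. Earlier censoring shortens the 393 days and raises the share.

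**Step 3. What does this imply for missed events?**

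The documents give neither a late-event rate nor a capture rate. Let c be the share of late events that is recorded. Assuming a constant event rate and no booster, the share of all events missed is (1 − c) × 336 / 393:

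| c | Late events missed | All events missed |
|---|---|---|
| 0 | 100% | 85.5% |
| 0.5 | 50% | 42.7% |
| 1 | 0% | 0% |

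The full range is open. The day counts measure time under collection, not events lost.

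**The case against.** The strongest reply is that nothing shows the data are incomplete. The 28-day sentence in protocol 9.1.1.2 describes how diaries are used, and prompts about health concerns are scheduled on Days 120 and 270. Subjects are asked about non-serious AEs at each visit. Most of the SAP presupposes whole-trial capture, and it is tied to eCRF version 5.0, which is not available here. If that form had a field for medically attended AEs, SAP 10.5.6 is simply correct. The third set of tables is openly labelled as what was reported. The primary endpoint uses 28 days and has its own tables, and the trial is descriptive: "No confirmatory statistical inference will be performed".

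Much of this stands. The protocol is contradictory rather than clearly limited to 28 days. Its silence on medically attended AEs does not show that they went uncollected. The primary-endpoint tables are sound.

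It does not dispose of the point. SAP 10.5.3 and the typed list of exceptions still give the opposite instruction. The passages that favour long collection mostly refer back to the diary or to Section 9.1.1. A label saying the events were reported does not tell a reader that recording may have been selective after 28 days.

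**Conclusion.** The concern holds as an unresolved contradiction with consequences for one set of tables. For medically attended and other non-serious unsolicited AEs, the whole-trial percentages in SAP 12.8.1 may be incomplete and may vary by site and booster status. If the 28-day limit governed, 14.5% of nominal follow-up was in scope without a booster and about 22% with one. The day counts assume nominal visit days and follow-up to Day 393.

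A reader might infer three stronger conclusions that the documents do not support:

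- *The protocol stops all non-serious AE collection at 28 days.* It does not. AESIs, intercurrent conditions and AEs leading to withdrawal are collected throughout even when non-serious, and Table 1 extends the unsolicited row further.
- *The whole-trial percentages leave out most late events or are biased downward by a known amount.* The missed share of late events could be anything from 0 to 100%. Any single figure would rest on an assumed event rate and an assumed capture rate.
- *Medically attended AEs were not collected.* What can be shown is that SAP 10.5.6 has no basis in the protocol text and is not declared in SAP 6.1.

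The matter should be settled before the final analysis, but it does not touch the 28-day safety tables.

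**What to change.** 1. Check what eCRF version 5.0 actually collected after 28 days, for ordinary unsolicited AEs and for medically attended AEs, and whether all sites collected it. Reconcile protocol 9.1.1.2 and Table 1 (with footnotes k and l) and SAP 10.5.2, 10.5.3, 10.5.6 and 12.8.1 with the result. Record any departure from the protocol in SAP 6.1.
2. In SAP 12.8.1, keep the whole-trial period only for event types collected systematically throughout: SAEs, AESIs, intercurrent conditions and AEs leading to withdrawal. Add medically attended AEs only if the eCRF captured them at all sites.
3. List late non-serious unsolicited AEs instead of tabulating them as percentages. Footnote any whole-trial table that is retained as incomplete beyond 28 days.
4. Do not shorten SAP 10.5.6 or the Table 1 row to 28 days unless the eCRF confirms that limit. Doing so without the form would choose one side of the conflict and could discard valid safety data.

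The cost is an eCRF check, SAP wording and fewer tables. The downside is that some late non-serious AEs appear in listings only.

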2 SCHEDULE OF ACTIVITIES

Table 1 Schedule of Trial Assessments and Procedures

Visit Number	Primary Vaccination Period								Booster Vaccination Period								End of Trial		
	1 ^a	2	Phone contact		3	Phone contact	4	Phone contact ^b	5 ^c	Phone contact ^c	6 ^c	Prompt	7	Phone contact ^d	8 ^d	Prompt	Phone contact	9 ^w	
Visit Window (days)	n/a	-0/ +0	-0/ +0	-2/ +4	-2/ +4	-0/ +0	-2/ +4	-2/ +4	-2/ +4	-0/ +0	-2/ +4	-2/ +4	-10/ +10	-0/ +0	-2/ +4	-2/ +4	-0/ +30	-0/ +30	
Trial Day	1	2	7 ^e	15	29	30	43	57	57	58	85	120	180	181	208	270	393	393	
Anchoring	-	1	1	1	1	29	29	29	57	57	57	29	1	180	180	180	180	180	
Signed informed consent	X																		
Inclusion/exclusion criteria	X																		
Demographics	X																		
Medical history	X																		
Vaccination																			
Review of criteria for delay or cancellation of vaccination ^f	X				X				X					X ^g					
Investigational vaccine administration (including 30-minute observation)	X				X				X					X ^g					
Safety Monitoring																			
Physical examination ^h	X ⁱ				X				X					X ^g					
Symptom-directed physical examination ^h		X				X				X						X			
Vital signs ^{h,j}	X	X			X		X		X		X		X		X		X		
ECG	X																		
Diary (re)training ^k	X	X			X		X		X					X ^g					
Diary review ^k		X	X	X	X	X	X	X		X	X				X	X			
Diary reminder ^k		X		X		X	X	X	X	X				X ^g	X				
Solicited AEs ^k	X	X		X	X	X	X	X	X	X	X			X ^g	X	X			
Unsolicited AEs ^k	X	X		X	X	X	X	X	X	X	X	X	X	X	X	X	X	X	X

Visit Number	Primary Vaccination Period								Booster Vaccination Period								End of Trial	
	1 ^a	2	Phone contact		3	Phone contact	4	Phone contact ^b	5 ^c	Phone contact ^c	6 ^c	Prompt	7	Phone contact ^d	8 ^d	Prompt	Phone contact	9 ^w
Visit Window (days)	n/a	-0/ +0	-0/ +0	-2/ +4	-2/ +4	-0/ +0	-2/ +4	-2/ +4	-2/ +4	-0/ +0	-2/ +4	-2/ +4	-10/ +10	-0/ +0	-2/ +4	-2/ +4	-0/ +30	-0/ +30
Trial Day	1	2	7 ^e	15	29	30	43	57	57	58	85	120	180	181	208	270	393	393
Anchoring	-	1	1	1	1	29	29	29	57	57	57	29	1	180	180	180	180	180
SAEs ^l	X	X		X	X	X	X	X	X	X	X	X	X	X	X	X	X	
Intercurrent medical conditions ^l	X	X		X	X	X	X	X	X	X	X	X	X	X	X	X	X	
AEs leading to premature discontinuation ^l	X	X		X	X	X	X	X	X	X	X	X	X	X	X	X	X	
AESIs ^l	X	X		X	X	X	X	X	X	X	X	X	X	X	X	X	X	
Concomitant medication/vaccination	X ^m	X		X	X	X	X	X	X	X	X	X	X	X	X	X	X	
Safety laboratory (~9 mL) ⁿ	X	X			X						X				X			
Safety laboratory in case of abnormal result at previous visit (~9 mL) ⁿ							X		X				X					
Serum pregnancy test (~3 mL) ^o	X																	
Urine pregnancy test ^o	X				X				X ^g				X ^g					
TSH, thyroid antibodies, ANA (~3 mL) ^o	X																	
Nasopharyngeal swab collection for RT-PCR testing ^q	X																	
Immunogenicity^r																		
ELISA (serum) (~12 mL) ^s	X ^t				X ^t		X		X ^t		X		X ^{t,v}		X		X	
Only in subjects in the initial phase of the trial: SARS-CoV-2 neutralizing activity (serum) (~12 mL)	X ^t				X ^t		X		X ^t		X		X ^{t,v}		X		X	

Visit Number	Primary Vaccination Period								Booster Vaccination Period								End of Trial	
	1 ^a	2	Phone contact		3	Phone contact	4	Phone contact ^b	5 ^c	Phone contact ^c	6 ^c	Prompt	7	Phone contact ^d	8 ^d	Prompt	Phone contact	9 ^w
Visit Window (days)	n/a	-0/ +0	-0/ +0	-2/ +4	-2/ +4	-0/ +0	-2/ +4	-2/ +4	-2/ +4	-0/ +0	-2/ +4	-2/ +4	-10/ +10	-0/ +0	-2/ +4	-2/ +4	-0/ +30	-0/ +30
Trial Day	1	2	7 ^e	15	29	30	43	57	57	58	85	120	180	181	208	270	393	393
Anchoring	-	1	1	1	1	29	29	29	57	57	57	29	1	180	180	180	180	180
Subset of subjects from each CVnCoV group at predefined site(s): Cell-mediated immunity (~40-64 mL) ^u	X ^t				X ^t		X											
Subset of subjects from each CVnCoV group at predefined site(s): Cytokine assessment (serum) (~6 mL)	X ^t	X																
Maximum total blood volume (mL)	109	15			73		73		33		33		33		33			33
Trial end																		X

AE: adverse event; AESI: adverse event of special interest; ANA: antinuclear antibody; ECG: electrocardiogram; ELISA: enzyme-linked immunosorbent assay; Ig: immunoglobulin; RT-PCR: reverse transcription polymerase chain reaction; SAE: serious adverse event; TSH: thyroid-stimulating hormone

- Procedures to establish subject eligibility may be performed within 21 days prior to trial vaccine administration. If all information to establish eligibility is available, these procedures can be done on the same day including the trial vaccine administration. Eligibility criteria need to be reviewed on the day of vaccination prior to trial vaccine administration.
- Phone contact on Day 57 is not required for subjects receiving an open-label booster vaccination on Day 57.
- This will only take place for subjects receiving an open-label booster vaccination on Day 57.
- This will only take place for subjects receiving an open-label booster vaccination on Day 180.
- Phone contact can be made on Day 7 at the site's discretion to review the eDiary with the subject, but is not mandatory, and does not replace other scheduled phone contacts
- See Section 6.3 for an overview of the criteria leading to delay or cancellation of vaccine administration. In case of delay, the vaccination should take place within the allowed time windows. The reasons for delay or cancellation should be documented in the subject chart.
- Only applicable for subjects receiving an open-label booster vaccination on Day 57/Day 180.
- Physical examination and vital signs must be performed/measured by a qualified healthcare professional. See Section 9.1.4 for an overview of the required assessments.
- If the complete physical examination to establish eligibility was performed within 21 days prior to trial vaccine administration, a symptom-directed physical examination should be performed on the day of vaccination prior to trial vaccine administration.
- Vital signs will be measured pre- and post-vaccination prior to discharge. Subjects will be observed for 30 minutes following each vaccination. Vital signs must be within normal or clinically non-relevant abnormal ranges or have returned to pre-vaccination values for the subject to be discharged.
- Solicited and unsolicited AEs will be recorded in diaries.
- SAEs, AESIs (including COVID-19 disease), intercurrent medical conditions that may affect the immune response to vaccination, and AEs leading to trial or trial vaccine withdrawal will be collected throughout the trial.
- Immunosuppressants or other immune-modifying drugs, with the exception of topically-applied, inhaled, or intranasal steroids, taken within 6 months prior to enrollment and any other concomitant medication/vaccination taken within 1 month prior to enrollment should be recorded to establish eligibility.

- n. See Appendix 3 for an overview of the safety laboratory assessments.
- o. A blood sample for serum pregnancy testing will be taken from women of childbearing potential on Day 1 prior to vaccination to establish eligibility. Urine pregnancy tests will be performed before each vaccination, unless the serum pregnancy test was performed less than 3 days before and yielded a negative result.
- p. A blood sample will be drawn for potential retrospective measurement of TSH, thyroid antibodies, and ANA in case of the occurrence of clinical autoimmune events during the trial (other autoantibodies might be investigated as well depending on the possible clinical autoimmune event).
- q. Swabs for COVID-19 disease testing will also be collected in case the subject displays symptoms of acute respiratory infection (including, but not limited to COVID-19 disease), if operationally possible (see Section 9.3).
- r. See Section 9.2 for an overview of the immunogenicity assessments.
- s. ELISA will be performed on SARS-CoV-2 spike (S) protein to investigate immune responses to vaccination and on SARS-CoV-2 nucleocapsid (N) protein to determine immune response to natural infection.
- t. Baseline blood samples on Day 1, Day 29, Day 57, and Day 180 must be collected prior to vaccination.
- u. The blood volume to be collected for cellular immune response will be 64 mL on Day 1 and 40 mL on Days 29 and 43.
- v. Only for subjects receiving 6 µg and for subjects receiving the 12 µg booster dose on Day 57 or Day 180.
- w. Only for subjects who received the booster on Day 180 and who had not received a licensed/authorized vaccine before the End of Trial visit.

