7.3 Randomization and Blinding

The initial phase of the trial will be conducted with 4 CVnCoV groups versus 2 active controls. In the initial phase, subjects will be randomized according to a 10:1 ratio to receive CVnCoV or the active control in an observer-blinded manner.

Subjects in the expansion cohorts will be randomized according to a 10:1 ratio to receive either the selected dose of CVnCoV or the active control in an observer-blinded manner; 200 subjects per age category will receive CVnCoV and 20 subjects will receive the active control.

The Sponsor and safety monitoring committees will be unblinded for data from the randomized groups, but will take appropriate measures to ensure subject blinding is kept at site level until database lock.

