9.2.2 Cell-Mediated Immunity

CMI will only be evaluated in approximately 20 subjects per CVnCoV group at assigned site(s).

The frequency and functionality of SARS-CoV-2 spike-specific T-cell response after antigen stimulation will be determined in PBMC in comparison to baseline. For example, ICS to investigate Th response will be used to investigate whether vaccination induces a Th1 shift from baseline. Further T-cell immune response may be investigated with other technologies like ELISpot or CyTOF.

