9.2.3 Innate Immune Response

The innate immune response will only be evaluated in approximately 20 subjects per CVnCoV group at assigned site(s) by measuring serum cytokines, including but not limited to IFN- α , IFN- γ , IL-6, CCL 2, and IP 10.

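### CMI and cytokine blood is planned only for CVnCoV recipients and starts before the first dose; followed as written, this discloses allocation in groups declared observer-blind

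*Protocol*

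**What the plan says.** In the Schedule of Activities (protocol section 2, Table 1), one immunogenicity row is headed "Subset of subjects from each CVnCoV group at predefined site(s): Cell-mediated immunity". The cytokine row carries the same restriction. There is no matching row for active-control subjects. The footnotes set the CMI volume at 64 mL on Day 1 and 40 mL on Days 29 and 43. The cytokine sample is 6 mL on Days 1 and 2. Another footnote fixes the timing: "Baseline blood samples on Day 1, Day 29, Day 57, and Day 180 must be collected prior to vaccination".

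Protocol 9.2.2 says "CMI will only be evaluated in approximately 20 subjects per CVnCoV group at assigned site(s", and 9.2.3 says the same of cytokines. SAP 9.4 and 10.6.5 repeat the figure of about 20 per CVnCoV group.

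Protocol 7.3 describes the initial phase as "4 CVnCoV groups versus 2 active controls", so a CVnCoV group is something other than a control group. Protocol 5.1 defines Groups 1 to 4 by receipt of CVnCoV and Groups 5 and 6 by receipt of a control vaccine, and marks all six as observer-blind for the primary doses. Section 7.3 also says that the Sponsor and the safety committees, who are unblinded, "will take appropriate measures to ensure subject blinding is kept at site level until database lock".

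**The concern.** If only CVnCoV recipients give this blood, someone must know a subject's allocation before the first dose in order to request the tubes. Even a bare instruction to draw them then means CVnCoV. The extra volume is plain to subject and staff: up to 109 mL on Day 1 against up to 39 mL without it. The absence of a draw at an assigned site also carries information, and it points towards control.

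The draws fall on Days 1, 2, 29 and 43, across the period in which the primary safety data are collected. The exposed outcomes are the solicited AEs that subjects record in diaries and the investigator's judgement of relationship for solicited systemic and unsolicited AEs. These are the outcomes an observer-blind design is meant to protect. The SAP itself treats knowledge of allocation as a source of bias: section 10.8 censors unblinded subjects for safety from the following day. It has no corresponding provision for subjects who could be identified on Day 1.

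**Working it through.** **1. Reproduce the plan's blood volumes.** Protocol section 9 gives maxima of 279 mL, or 435 mL for subjects with CMI and cytokine assessment. Summing the last row of Table 1: 109 + 15 + 73 + 73 + (5 × 33) = 435 mL. CMI plus cytokine blood: (64 + 40 + 40) + (6 + 6) = 156 mL. Then 435 − 156 = 279 mL. Both figures reproduce.

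The two maxima therefore differ by exactly this blood, so collection differs between subjects, not only the assay. By visit, with and without it:

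| Day | With | Without |
|---|---|---|
| 1 | 109 mL | 39 mL |
| 2 | 15 mL | 9 mL |
| 29 | 73 mL | 33 mL |
| 43 | 73 mL | 33 mL |

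The volumes show that a subset gives more blood. That the subset is defined by vaccine comes from the row labels and from 9.2.2 and 9.2.3.

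**2. What a draw discloses.** At 10:1 allocation, P(CVnCoV) = 10/11 = 90.9% before any draw. If only CVnCoV recipients are drawn, P(CVnCoV given drawn) = 100%.

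**3. What the absence of a draw discloses.** Let m be the number of CVnCoV subjects of one 12 µg group at assigned sites, with m/10 controls there and 20 subjects drawn. Then P(control given not drawn) = (m/10) / (m/10 + m − 20), against 1/11 = 9.1% beforehand. The documents do not give m, so a range is assumed:

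| m | Calculation | P(control) |
|---|---|---|
| 90 | 9/79 | 11.4% |
| 45 | 4.5/29.5 | 15.3% |
| 30 | 3/13 | 23.1% |
| 20 | 2/2 | 100% |

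Groups 1 and 2 have 11 and 12 CVnCoV subjects, fewer than 20, and one control each. If all were at assigned sites and every CVnCoV subject were drawn, that single control would be identified.

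**4. How many subjects.** Initial-phase CVnCoV subjects: 11 + 12 + 90 + 90 = 203. Drawn, at most: 11 + 12 + 20 + 20 = 63, and 63/203 = 31%. This takes approximately 20 as 20, assumes the same subjects give both samples (as the single 435 mL total suggests), and leaves out the expansion cohorts. Those have no group number, so it is unclear whether they count as CVnCoV groups.

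**5. Illustration of size.** Assume that going from certainty of control to certainty of CVnCoV raises reported or related AEs by 10 percentage points (range 5 to 15), in proportion to perceived probability. Neither assumption comes from the documents.

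- A drawn subject shifts by 10 × 1/11 = 0.9 points.
- In the worst case of step 3, the identified controls number 1 + 1 + 2 + 2 = 6. Each shifts down by 10 × 10/11 = 9.1 points.
- Initial phase alone: CVnCoV rises by 0.91 × 63/203 = 0.3, and controls fall by 9.1 × 6/20 = 2.7. The gap is about 3.0 points (range 1.5 to 4.5).
- Initial and expansion subjects together, as SAP 12.0 presents them, with no expansion draws: 0.91 × 63/603 = 0.1 and 9.1 × 6/60 = 0.9. The gap is about 1.0 point (range 0.5 to 1.5).

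For scale, an approximate 95% interval for a proportion near 50% in 60 controls has half-width 1.96 × √(0.25/60) = 13 points.

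**The case against.** **The text may allow a masked procedure.** Sections 9.2.2 and 9.2.3 speak of evaluating subjects, not drawing them, and the Sponsor undertakes to protect the site blind. Bleeding everyone at the assigned sites and assaying only CVnCoV samples would fit those two sections. It fits Table 1 less well, because Table 1 schedules procedures and applies the restriction to the draw. Still, a laboratory or site manual could provide masking. The documents are silent on this, so they do not establish that any site or subject was in fact unblinded, although a reader might infer it.

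**The term CVnCoV group is used loosely.** The footnote to protocol Table 5 counts one control from each of Groups 1 and 2, as if controls sat inside those groups. This conflicts with the definitions in 5.1 and the contrast in 7.3. It is a reason to clarify the wording; it does not show that controls were meant to be drawn.

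**Allocation was already easy to guess.** This stands. At 91% beforehand, the draw adds little for a CVnCoV recipient. The larger change is for the few controls who are not drawn.

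**Some outcomes are robust.** This also stands. Solicited local AEs are related by definition, and redness and fever are graded by measurement. The trial is descriptive throughout.

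**Everyone is unblinded under protocol version 3.0.** That does not answer the point for data from Days 1 to 43, when the site blind was meant to hold.

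**A stronger reading concerns dose.** The whole 6 µg cohort could be drawn, but only 40 of 580 (7%) at 12 µg. A reader might infer a false dose difference of 10 × (1 − 0.069) = 9.3 points. The documents do not support that. It ignores the 91% starting probability; scaled for this, the figure is 10/11 × (1 − 0.069) = about 0.8 points. It takes all 23 subjects at 6 µg as drawn, which is a worst case. And under protocol 5.1 the two dose levels were enrolled one after the other, so 6 versus 12 µg was never a concealed randomised comparison.

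**Conclusion.** The inconsistency is real. As written, the sampling plan ties a visible pre-dose procedure to receipt of CVnCoV, in groups whose blind is to be kept at site level. A drawn subject is disclosed as a CVnCoV recipient, and an undrawn subject at an assigned site becomes more likely to be a control, in the limit certainly so. The 63 of 203 is an upper bound that rests on the assumptions in step 4 of the working.

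The comparison affected is CVnCoV versus control, for diary-reported solicited AEs and for investigator-judged relationship of systemic and unsolicited AEs. The size of any bias cannot be derived from the documents. Under the stated assumptions it is small beside the sampling error of the control arm, even in the worst case. No claim is made about 6 versus 12 µg, nor that unblinding actually took place. The point matters because the blind is a stated design feature and the plan neither protects it here nor examines the consequence.

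**What to change.** **Wording.** In Table 1, 9.2.2 and 9.2.3, select the subset from randomised subjects at the predefined sites regardless of arm, with allocation known only to the laboratory or unblinded Sponsor staff. At 10:1 this adds about 63/10 = 6 controls, each giving up to 156 mL more blood. The draw then discloses nothing: with 20 of 90 CVnCoV subjects and 2 of 9 controls drawn, P(CVnCoV given drawn) = 20/22 = 90.9%, the same as before the draw. It also gives the CMI and cytokine data a control reference. If the draws were in fact masked, one sentence recording how would close the point.

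**Analysis.** SAP 11.1 reports interim analyses already done, including booster data to Day 208, so new wording cannot change samples already taken. Where only CVnCoV recipients were sampled, add to SAP 12.8.1 and 12.8.2 a sensitivity repeat of the solicited-AE and related-AE tables for CVnCoV versus control, excluding the CMI/cytokine subset. Report that the blind may have been compromised in that subset and at the assigned sites. SAP 6.0 allows amendment before final database lock.

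**Cost and limits.** The cost is one extra set of tables from existing data. The repeat still includes undrawn controls at the assigned sites, which is why the reporting statement is needed as well. It may also leave few or no 6 µg subjects, so it cannot inform any dose comparison.
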